8.3.8 Hy’s law

Cases where a patient shows elevations in liver biochemistry may require further evaluation and occurrences of AST or ALT $\geq 3xULN$ together with total bilirubin $\geq 2xULN$ may need to be reported as SAEs. Please refer to 0 for further instruction on cases of increases in liver biochemistry and evaluation of Hy’s Law

8.3.9 Disease-under study (DUS)

Symptoms of DUS are those which might be expected to occur as a direct result of ES-SCLC or procedures to diagnose or treat ES-SCLC . Events which are unequivocally due to disease under

study should not be reported as an AE during the study unless they meet SAE criteria or lead to discontinuation of the investigational product.

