The incidence of common, or uncommon (<1%) serious adverse events will be estimated. Serious adverse events, grade 3/4 AEs, AE leading to death, AE leading to discontinuation, imAE and adverse events of special interest will be summarised by preferred term and incidence rates.

[figure not shown]
Baseline will be the last assessment of the variable under consideration prior to the intake of the first study drug (Durvalumab) dose.

Planned subgroup analyses of safety and effectiveness according to baseline characteristics include: ECOG status, gender, , presence of brain or liver metastases, smoking status, age of 65 years or older, and use of prophylactic cranial irradiation.

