8.3.6 Adverse events based on signs and symptoms

All AEs spontaneously reported by the patient or reported in response to the open question from the study site staff, or revealed by observation will be collected and recorded in the CRF. When collecting AEs, the recording of diagnoses is preferred (when possible) to recording a list of signs and symptoms. However, if a diagnosis is known and there are other signs or symptoms that are not generally part of the diagnosis, the diagnosis and each sign or symptom will be recorded separately.

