Appendix B Adverse event definitions and additional safety information

B 1 Definition of adverse events

An adverse event is the development of any untoward medical occurrence (other than progression of the malignancy under evaluation) in a patient or clinical study patient administered a medicinal product and which does not necessarily have a causal relationship with this treatment. An AE can therefore be any unfavorable and unintended sign (eg, an abnormal laboratory finding), symptom (for example nausea, chest pain), or disease temporally associated with the use of a medicinal product, whether or not considered related to the medicinal product.

The term AE is used to include both serious and non-serious AEs and can include a deterioration of a pre-existing medical occurrence. An AE may occur at any time, including run-in or washout periods, even if no Study treatment has been administered.

B 2 Definitions of serious adverse event

A serious adverse event is an AE occurring during any study phase (ie, run-in, treatment, washout, follow-up), that fulfils one or more of the following criteria:

- Results in death
- Is immediately life-threatening
- Requires in-patient hospitalization or prolongation of existing hospitalization
- Results in persistent or significant disability or incapacity.
- Is a congenital abnormality or birth defect
- Is an important medical event that may jeopardize the patient or may require medical treatment to prevent one of the outcomes listed above.

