#### Endpoints analyzed:

- Incidence of grade  $\geq 3$  AEs
- Incidence of imAE.

This analysis will be performed for Safety analysis set. For all summaries of AEs, only treatment-emergent AEs will be included. Treatment-emergent AEs are defined as events present at baseline that worsen in intensity after administration of IP or events absent at baseline that emerge after administration of IP, for the period extending to 90 days after the last dose of IP.

The analysis will be performed with the information completed into the adverse event eCRF section.

Total SAEs, AESIs, AEs leading to death, and AEs leading to study drug interruption or discontinuation will be summarized by Medical Dictionary for Regulatory Activities (MedDRA) by System Organ Class (SOC) and Preferred Term (PT), causality, and maximum NCI CTCAE Grade. Deaths from all causes will be also summarized.

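### Protocol 8.3.9 folds effects of diagnostic and treatment procedures into the symptoms of disease that sites are told not to report, so non-serious Grade ≥3 effects of PCI or radiotherapy can be missing from the primary endpoint

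*Protocol*

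**What the plan says.** Protocol 8.3.9 consists of a definition and a bar.

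- Definition: symptoms of the disease under study are those which "might be expected to occur as a direct result of ES-SCLC or procedures to diagnose or treat ES-SCLC".
- Bar: the sentence that opens "Events which are unequivocally due to disease under" keeps such events off the AE form, with two exceptions: the event is serious, or it causes the investigational product to be stopped.

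Protocol 8.3.7 exempts a new or aggravated physical-examination finding from AE reporting when it is unequivocally related to the disease under study, and refers the reader to 8.3.9 and 8.3.10.

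Two other places are wider. Appendix B 1 defines an AE as "any untoward medical occurrence (other than progression of the malignancy under evaluation"), so progression is its only exclusion. Section 8.3.6 collects "All AEs spontaneously reported by the patient or reported in response to the open question from the study site staff, or revealed by observation".

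For the primary outcome, SAP 4.2.1 states: "The analysis will be performed with the information completed into the adverse event eCRF section". It names no other source.

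PCI is permitted in patients with a complete or partial response (Protocol 4.1 and Table 6), and palliative radiotherapy to non-target lesions is permitted (Table 7). The synopsis lists "smoking status, age of 65 years or older, and use of prophylactic cranial irradiation" among the factors for planned subgroup analyses of safety and effectiveness.

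**The concern.** The primary objective is to describe safety, and one of the two primary endpoints is the incidence of Grade ≥3 AEs. A rule that narrows what is entered on the AE form therefore narrows the endpoint.

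PCI and palliative radiotherapy are naturally read as procedures that treat ES-SCLC. Take a responder on durvalumab maintenance who has a non-serious Grade 3 headache after PCI. One site follows Appendix B 1 and records it. Another reads the 8.3.9 definition into the bar, judges the headache an expected effect of a procedure to treat the cancer, and records nothing. Both can point to the protocol.

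Two things are at stake. First, the incidence can be understated, in one direction only, and the exact confidence interval does not allow for this. Second, part of any difference in rates between sites could come from how the clause was read. The study rationale (Protocol 2.1) names patients in whom PCI may be expected to help among those with limited effectiveness and safety information, so this is toxicity the study has reason to capture.

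**Working it through.** **Does the bar reach procedure effects?** The bar names the disease under study and does not mention procedures. Procedures enter only through the definition in the sentence before. Section 8.3.9 contains nothing else, so the definition has no evident use except to set the scope of the bar. Section 8.3.7 sends sites to 8.3.9 when deciding whether an examination finding is exempt. Progression has its own section, 8.3.10, so the procedure wording is not a restatement of that exemption. Carrying the definition into the bar is thus a reasonable reading, though not the only one.

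**Can a barred event be Grade ≥3?** Yes. Appendix B 6 separates severity from seriousness and says a severe event need not be serious. An event that is Grade 3, non-serious and does not stop the investigational product meets neither exception.

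**Would it otherwise have counted?** SAP 4.2.1 counts treatment-emergent AEs up to 90 days after the last dose. PCI given after the combination cycles, and radiotherapy given on study, normally fall in that window. Effects of a diagnostic procedure done and finished before the first dose would not be counted in any case, so the diagnostic part matters mainly for procedures during treatment.

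**The plan's own figure.** Inputs from Protocol 9.2: n = 85, assumed Grade ≥3 incidence 70%, exact (Clopper-Pearson) 95% interval. Limits for x events:

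- lower = 2.5% quantile of Beta(x, n − x + 1)
- upper = 97.5% quantile of Beta(x + 1, n − x)

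0.70 × 85 = 59.5. With x = 60 the interval is 59.7% to 80.0%, half-width 10.1 points. This reproduces the protocol's 59.7–80.0; the half-width is printed there as ±10.0%.

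**Effect of omission.** A patient counts once, so an omitted event matters only if it was that patient's only Grade ≥3 AE. If k such patients are lost, the shift is −k/85. One patient: 1/85 = 1.2 points. Starting from 60/85:

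| Patients lost (k) | Observed | Incidence | Exact 95% CI | Shift (points) |
|---|---|---|---|---|
| 0 | 60/85 | 70.6% | 59.7–80.0 | 0 |
| 2 | 58/85 | 68.2% | 57.2–77.9 | −2.4 |
| 5 | 55/85 | 64.7% | 53.6–74.8 | −5.9 |
| 10 | 50/85 | 58.8% | 47.6–69.4 | −11.8 |

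The shift passes the stated 10-point precision at k = 9 (9/85 = 10.6; 8/85 = 9.4). The values of k are assumptions chosen to show the scale; the documents supply none. If more than 85 patients are recruited, as 9.2 allows, each lost patient weighs less.

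**The case against.** The strongest reply is that the bar covers only events unequivocally due to the disease. Headache or fatigue after PCI in a patient who is also receiving durvalumab is hard to call unequivocally due to ES-SCLC. A careful site, reading Appendix B 1 and 8.3.6 as well, would record it. This stands as a limit on the claim: the text creates an ambiguity and does not settle the matter against reporting. It does not remove the problem, because the definition beside the bar tells sites that procedure effects belong to the disease, and no section ranks one rule above the other.

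Several stronger readings are tempting, and the documents do not support them.

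- *All procedure toxicity is lost, so the PCI count is zero by rule.* Serious events and events that stop the investigational product are still reported, and the test of being unequivocal leaves others reportable.
- *The clause also exempts effects of the study infusions.* Section 8.3.13 makes infusion-related and hypersensitivity reactions AEs of special interest, 8.2.3 sets a recording rule for AEs of infusion reactions, and 8.4.5 grades all toxicities by CTCAE.
- *Unreported events leave no trace.* PRO-CTCAE and the EORTC questionnaires, completed on day 1 of every cycle, can capture some symptoms, fatigue among them. They do not feed the Grade ≥3 count.
- *The planned PCI safety comparison is biased.* Only the synopsis lists that subgroup. Protocol 9.5.1 and SAP 5.1 omit it and make their subgroup analyses optional, and SAP 4.3.4.1 only counts PCI recipients. If the comparison is run, the same under-recording would affect it.
- *The loss can be estimated from the response rate.* The figure of up to 70% in the introduction is a historical response to chemotherapy. It bears on who might be eligible for PCI, not on who receives it or what toxicity follows.

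**Conclusion.** The point holds as a contradiction between sections that can reduce the primary endpoint. Section 8.3.9, with the pointer from 8.3.7, allows non-serious, non-discontinuing Grade ≥3 effects of PCI, palliative radiotherapy or on-study diagnostic procedures to be left off the AE form. Section 8.3.6 and Appendix B 1 call for recording them. The consequence rests on two conditions: that some sites read the definition into the bar, and that some patients have such an event as their only Grade ≥3 AE. The documents do not show how often either happens.

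The size is therefore unknown. What can be stated is the scale of 1.2 points per affected patient at n = 85, and the direction, which is always downward. A few such patients would move the estimate by less than the planned precision; about nine would exceed it. In a descriptive study without hypotheses this should be fixed but does not invalidate the plan. The case for acting is that the bias is one-directional, and events never recorded may not be recoverable at analysis.

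**What to change.** In Protocol 8.3.9, delete the reference to diagnostic and treatment procedures, so that the definition covers only direct effects of the cancer. Add one sentence saying that effects of study treatment, PCI, radiotherapy and study or treatment procedures are recorded and graded as AEs.

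Then reconcile 8.3.6, 8.3.7, 8.3.9 and Appendix B 1. The deletion alone does not align them: 8.3.9 would still exempt non-serious symptoms of the cancer, whereas Appendix B 1 excludes only progression. The protocol should state one rule and repeat it in the eCRF completion guidance. The subgroup lists in the synopsis, Protocol 9.5.1 and SAP 5.1 should also agree on whether safety by PCI use will be analysed.

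The cost is a short protocol and eCRF-guidance change, slightly more AE entry at sites, and possibly a slightly higher reported Grade ≥3 incidence. Patient management does not change.

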8.3.10 Disease progression

Disease progression can be considered as a worsening of a patient's condition attributable to the disease for which the investigational product is being studied. It may be an increase in the severity of the disease under study and/or increases in the symptoms of the disease. The development of new, or progression of existing metastasis to the primary cancer under study should be considered as disease progression and not an AE. Events, which are unequivocally due to disease progression, should not be reported as an AE during the study.

8.3.11 New cancers

The development of a new cancer should be regarded as an SAE. New primary cancers are those that are not the primary reason for the administration of the IP and have been identified after the patient's inclusion in this study.

8.3.12 Deaths

All deaths that occur during the study treatment period, or within the protocol-defined follow-up period after the administration of the last dose of study drug, must be reported as follows:

- Death clearly resulting from disease progression should be reported to the Study Monitor/Physician at the next monitoring visit and should be documented in the eCRF Death page. It should not be reported as an SAE.
- Where death is not due (or not clearly due) to progression of the disease under study, the AE causing the death must be reported to the Study Monitor/Physician as an SAE within 24 hours. It should also be documented in the Death page in the eCRF. The report should contain a comment regarding the co involvement of PD, if appropriate, and should assign main and contributory causes of death.
- Deaths with an unknown cause should always be reported as an SAE. It should also be documented in the Death page in the eCRF. A post mortem may be helpful in the assessment of the cause of death, and if performed, a copy of the post-mortem results should be forwarded to AstraZeneca Patient Safety or its representative within the usual timeframes.

Deaths occurring after the protocol defined safety follow up period after the administration of the last dose of study drug should be documented in the Death page. If the death occurred as a result of an event that started post the defined safety follow up period and the event is considered to be due to a late onset toxicity to study drug then it should also be reported as an SAE.

8.3.13 Adverse events of special interest

An adverse event of special interest (AESI) is one of scientific and medical interest specific to understanding of the Investigational Product and may require close monitoring. An AESI may be serious or non-serious. The rapid reporting of AESIs allows ongoing surveillance of these events

in order to characterize and understand them in association with the use of this investigational product.

AESIs for durvalumab include but are not limited to events with a potential inflammatory or immune-mediated mechanism and which may require more frequent monitoring and/or interventions such as steroids, immunosuppressants and/or hormone replacement therapy. These AESIs are being closely monitored in clinical studies with durvalumab monotherapy and combination therapy. An immune-mediated adverse event (imAE) is defined as an AESI that is associated with drug exposure and is consistent with an immune-mediated mechanism of action and where there is no clear alternate etiology. Serologic, immunologic, and histologic (biopsy) data, as appropriate, should be used to support an imAE diagnosis. Appropriate efforts should be made to rule out neoplastic, infectious, metabolic, toxin, or other etiologic causes of the imAE.

If the Investigator has any questions in regards to an event being an imAE, the Investigator should promptly contact the Study Physician.

AESI/imAEs observed with anti PD-L/PD-1 agents such as durvalumab include pneumonitis, hepatitis, diarrhea/colitis, intestinal perforation, endocrinopathies (hypo- and hyper-thyroidism, adrenal insufficiency, hypophysitis/hypopituitarism and Type 1 diabetes mellitus), nephritis, rash/dermatitis, myocarditis, myositis/polymyositis, pancreatitis and rare/less frequent imAEs including neuromuscular toxicities such as myasthenia gravis and Guillain-Barre syndrome.

Other inflammatory responses that are rare/less frequent with a potential immune-mediated etiology include, but are not limited to, pericarditis, sarcoidosis, uveitis, and other events involving the eye, skin, hematological, rheumatological events, vasculitis, non-infectious meningitis and non-infectious encephalitis. It is possible that events with an inflammatory or immune mediated mechanism could occur in nearly all organs

In addition, infusion-related reactions and hypersensitivity/anaphylactic reactions with a different underlying pharmacological etiology are also considered AESIs.

Further information on these risks (eg, presenting symptoms) can be found in the current version of the durvalumab IB. More specific guidelines for their evaluation and treatment are described in detail in the Dose Modification and Toxicity Management Guidelines (see Section 8.4.5). These guidelines have been prepared by the Sponsor to assist the Investigator in the exercise of his/her clinical judgment in treating these types of toxicities. These guidelines apply to AEs considered causally related to the study drug/study regimen by the reporting Investigator.

8.3.14 Safety data to be collected following the final DCO of the study

For patients continuing to receive durvalumab treatment after final DCO and database closure, it is recommended that the patients continue the scheduled site visits and Investigators monitor the patient's safety laboratory results prior to and periodically during treatment with durvalumab in order to manage AEs in accordance with the durvalumab Dose Modification and Toxicity Management Guidelines (see Section 8.4.5). All data post the final DCO and database closure will be recorded in the patient notes but, with the exception of SAEs, will not otherwise be reported for the purposes of this study.

All SAEs that occur in patients still receiving durvalumab treatment (or within the 90 days following the last dose of durvalumab treatment) post the final DCO and database closure must be reported as detailed in Section 8.4.1.

8.4 Safety reporting and medical management

8.4.1 Reporting of serious adverse events

All SAEs have to be reported, whether or not considered causally related to the investigational product, or to the study procedure(s). All SAEs will be recorded in the CRF.

If any SAE occurs in the course of the study, then Investigators or other site personnel inform the appropriate AstraZeneca representatives within one day (ie, immediately but **no later than 24 hours** of when he or she becomes aware of it).

The designated AstraZeneca representative works with the Investigator to ensure that all the necessary information is provided to the AstraZeneca Patient Safety data entry site **within 1 calendar day** of initial receipt for fatal and life threatening events **and within 5 calendar days** of initial receipt for all other SAEs.

For fatal or life-threatening adverse events where important or relevant information is missing, active follow-up is undertaken immediately. Investigators or other site personnel inform AstraZeneca representatives of any follow-up information on a previously reported SAE within one calendar day (ie, immediately but **no later than 24 hours** of when he or she becomes aware of it).

Once the Investigators or other site personnel indicate an AE is serious in the EDC system, an automated email alert is sent to the designated AstraZeneca representative.

If the EDC system is not available, then the Investigator or other study site staff reports a SAE to the appropriate AstraZeneca representative by telephone.

The AstraZeneca representative will advise the Investigator/study site staff how to proceed. For further guidance on the definition of a SAE, see Appendix B of the Clinical Study Protocol.

8.4.2 Pregnancy

All pregnancies and outcomes of pregnancy should be reported to AstraZeneca except for:

- If the pregnancy is discovered before the study patient has received any study drug

If a pregnancy is reported, the Investigator should inform the Sponsor within 24 hours of learning of the pregnancy.

Abnormal pregnancy outcomes (eg, spontaneous abortion, fetal death, stillbirth, congenital anomalies, ectopic pregnancy) are considered SAEs.

8.4.2.1 Maternal exposure

If a patient becomes pregnant during the course of the study, study treatment should be discontinued immediately.

Pregnancy itself is not regarded as an adverse event unless there is a suspicion that the investigational product under study may have interfered with the effectiveness of a contraceptive medication. Congenital abnormalities/birth defects and spontaneous miscarriages should be reported and handled as SAEs. Elective abortions without complications should not be handled as AEs. The outcome of all pregnancies (spontaneous miscarriage, elective termination, ectopic pregnancy, normal birth or congenital abnormality) should be followed up and documented even if the patient was discontinued from the study.

If any pregnancy occurs in the course of the study, then the Investigator or other site personnel informs the appropriate AstraZeneca representatives within 1 day (ie, immediately but **no later than 24 hours** of when he or she becomes aware of it).

The designated AstraZeneca representative works with the Investigator to ensure that all relevant information is provided to the AstraZeneca Patient Safety data entry site within 1 or 5 calendar days for SAEs (see Section 8.4.1) and within 30 days for all other pregnancies.

The same timelines apply when outcome information is available.

8.4.2.2 Paternal exposure

Male patients should refrain from fathering a child or donating sperm during the study and for 90 days after the last dose of durvalumab + EP combination therapy or 90 days after receipt of the final dose of durvalumab maintenance therapy.

Pregnancy of the patient's partner is not considered to be an AE. However, the outcome of all pregnancies (spontaneous miscarriage, elective termination, ectopic pregnancy, normal birth, or congenital abnormality) occurring from the date of the first dose until 90 days after the last dose of durvalumab + EP combination therapy or 90 days after receipt of the final dose of durvalumab maintenance therapy should, if possible, be followed up and documented.

Where a report of pregnancy is received, prior to obtaining information about the pregnancy, the Investigator must obtain the consent of the patient's partner. Therefore, the local study team should adopt the generic ICF template in line with local procedures and submit it to the Ethics Committees (ECs) prior to use.

Patients who are permanently discontinued from further receipt of IP, regardless of the reason, will be identified as having permanently discontinued treatment and will enter follow-up (see the SoAs).

